1.2 Description of MEDI-546

MEDI-546 is a fully human IgG1 kappa (IgG1 κ) monoclonal antibody directed against type I IFNAR1. MEDI-546 is composed of 2 light chains and 2 heavy chains, with an overall molecular weight of approximately 148 kDa.

The biological activity of MEDI-546 is quantified relative to Reference Standard using a binding enzyme-linked immunosorbent assay (ELISA) and a bioassay. The ELISA measures the binding of MEDI-546 to IFNAR. The cell-based bioassay measures the inhibition of IFN- α - induced signaling activity resulting from the binding of MEDI-546 to cell surface IFNAR.

1.3 Nonclinical Experience with MEDI-546

MEDI-546 blocks the binding of type I IFN to IFNAR and inhibits the biologic activity of all type I IFN subtypes. MEDI-546 does not have agonistic activity and is devoid of Fc γ RI,

Fc γ RIIA, Fc γ RIIB Fc γ RIIIA, and C1q binding activity. Therefore, MEDI-546, does not induce ADCC and CDC. With the growing evidence that type I IFNs play an important role in autoimmune diseases such as scleroderma, SLE, and myositis, inhibition of the biological activity of type I IFNs with MEDI-546 may, therefore, be a novel therapy for the treatment of these diseases with significant unmet medical need

Cynomolgus monkey was selected as the pharmacologically relevant animal species for nonclinical safety assessment based on binding affinity and neutralization activity of MEDI-546 in monkey cells. MEDI-546 does not cross-react with murine IFN- α .

The preliminary non-Good Laboratory Practice (GLP) single intravenous (IV) infusion receptor occupancy study was designed to evaluate safety and receptor occupancy at toxicologically relevant MEDI-546 dose levels (5, 30, or 100 mg/kg). There was no evidence of MEDI-546 toxicity after a single 30-minute IV infusion on Day 1 up to 100 mg/kg (single dose no-observable-adverse-effect-level [NOAEL]), the highest dose tested. Anti-MEDI-546 antibodies were detected in most animals following a single dose, with the frequency inversely proportional to the dose level administered and increasing at later time points. Clinical observations consistent with a hypersensitivity reaction occurred in 1 of 3 animals that received repeat MEDI-546 doses (5 mg/kg) on Days 37 and 50, with the intensity of the clinical response greatest at the Day 50 (third) administration. This monkey's symptoms were relieved by administration of IV antihistamine (Benadryl[®]) with no further observations through the end of the study. Investigative and exploratory analyses (cytokine analysis and isotyping and specificity characterization of the anti-MEDI-546 antibody response) were conducted in an effort to identify the underlying mechanism of the apparent hypersensitivity response. While the IgE, IgA, and IgM classes were assessed, the major isotype of anti-MEDI-546 antibody is anticipated to be IgG (IgG could not be assessed due to technical limitations in the isotyping assay). Isotyping analysis showed that only the animal with clinical symptoms following re-dose possessed a detectable IgE response against MEDI-546 on Days 22 and 29 prior to re-dosing (IgM was also detected for this animal on Day 22) and all three re-dosed animals had detectable IgE antibody by Day 70 following the 2 additional MEDI-546 doses. Results of specificity characterization and cytokine analysis did not show any clear correlation with hypersensitivity potential. This isolated case of hypersensitivity-like reaction was not reproducible in the subsequent 1-month repeated IV infusion dose toxicity study (described in more detail below).

A GLP single IV infusion dose study was conducted using MEDI-546 dose levels (0.003, 0.03, 0.3, or 1 mg/kg) chosen to evaluate safety and receptor occupancy at pharmacologically

relevant doses and to determine the minimum dose at which no receptor occupancy is detected. There were no adverse MEDI-546-related observations during the 28-day study period. Immunogenicity results showed evidence of anti-MEDI-546 antibodies in the majority of MEDI-546-dosed animals. Receptor occupancy analysis and PD analysis by in vitro genomic assay (IFN-inducible gene expression profile in whole blood samples) suggested the MEDI-546 doses administered in this study were in a pharmacologically active range.

A non-GLP single (IV) or subcutaneous (SC) dose toxicity study was conducted using a 5 mg/kg MEDI-546 dose level chosen to evaluate safety PK, PD, and IM (Study No. 7140-142, Covance Laboratories, Inc, Vienna, VA). In this study, one group of 3 male animals received a single 30-minute IV infusion of 5 mg/kg MEDI-546, while the other group received a single subcutaneous injection of 5 mg/kg MEDI-546. Animals were observed for 28 days to assess the reversibility, persistence, or delayed occurrence of effects. There was no control group comparator or necropsy in this study. Assessment of toxicity was based on mortality, clinical signs (including food consumption), dermal observation of the injection/infusion site, physical examinations, and body weight.

There were no observations of systemic or dermal toxicity or remarkable differences between the effects of the two routes of exposure. Pharmacodynamic activity was evident with the strongest target neutralization observed at Day 2 for intravenously dosed animals and Day 8 for subcutaneously dosed animals. The absolute bioavailability of MEDI-546 could not be determined, most likely due to variability influenced by the small sample size in this study. Similar titer values of anti-MEDI-546 antibody were detected by Day 29 for all animals, regardless of dose route.

A GLP 1-month repeated IV infusion dose toxicity study in cynomolgus monkeys was conducted using MEDI-546 dose levels (0.5, 5, or 30 mg/kg/dose) chosen to evaluate safety at toxicologically relevant doses when administered weekly for 4 total administrations. No adverse MEDI-546-related changes (including hypersensitivity-like reactions) in toxicological end points were noted during the 70-day study period. The NOAEL of MEDI-546 after 4 once-weekly IV infusions to cynomolgus monkeys was considered to be 30 mg/kg, the highest dose tested.

A GLP 9-month repeat dose toxicity study was conducted in cynomolgus monkeys (6/sex/dose group) where MEDI-546 was administered by IV infusion or subcutaneous (SC) injection at the dose levels (0, 5, 50, 15, 60 mg/kg/dose), once weekly for 39 weeks. The

control group received once weekly IV infusion and SC injection of formulation buffer. Necropsies were performed three days (terminal) or 13 weeks (recovery) following the final dose. Toxicity was assessed based on physical examination and clinical signs, dermal irritation, body weight, qualitative food consumption, ophthalmic exam, electrocardiographic (ECG), blood pressure, semen analysis, immunophenotyping, hematology, coagulation, clinical chemistry, urinalysis, organ weight, macroscopic and microscopic parameters.

Though all of the data for the study are not yet available at this time, there have been no unscheduled deaths and no MEDI-546-related adverse changes in clinical signs, physical examination, dermal irritation, body weight, qualitative food consumption, ophthalmic examination, electrocardiographic, blood pressure, semen analysis, hematology, coagulation, clinical chemistry, urinalysis, organ weight, or macroscopic parameters. In a total of 5 male animals (5/24, 21%) and 0 female animals (0/24, 0%) exposed to MEDI-546, microscopic examination found signs of focal arteritis in small and medium sized arteries. The severity grades of the arteritis ranged from 1 to 3 on a 5-point scale, with Grade 2 findings most frequent and reflected both the intensity of the change as well as the overall distribution in the tissue (number of vessels affected). The arteritis was manifest primarily by intramural and perivascular infiltrates of lymphocytes and macrophages, without necrosis, giant cells or granulomas. Several tissue types/organs were affected, the kidney and gut most frequently, and there were no lesions in kidney glomeruli. Findings were less pronounced and generally less widespread in recovery necropsy animals following a 13 week dose free period when compared to the terminal necropsy animals. Though a vasculitis background incidence of 1-6% has been noted in the literature for this species, no control animal tissues showed vascular pathology and there were no other significant pathology findings attributable to MEDI-546 administration.

The relevance of these findings to human treatment with MEDI-546 is not definitely known at this time. Due to the immunogenicity (high ADA titers) of MEDI-546 in primates, the current hypothesis is that the vascular findings are likely the result of a chronic immune-mediated reaction in the animals, involving antigen-antibody complexes. This will be explored with further testing of the toxicology study tissue samples. The development of ADA in animals is common and does not accurately predict responses in humans. One recent literature abstract describes similar vascular lesions in monkeys dosed with a monoclonal antibody, that were considered likely due to deposits of ADA/drug complexes.¹ While animal immune responses do not accurately predict responses in humans, the vascular findings in the present study may indicate an increased risk to patients of immune-mediated

adverse effects with MEDI-546 treatment, such as the risk of hypersensitivity reactions or immune-complex reactions, including vasculitis.

In cynomolgus monkeys, MEDI-546 showed a biphasic serum disposition profile. No appreciable gender difference was observed. In general, the maximum observed serum concentration (C_{max}) was dose proportional, while a more than dose-proportional increase in the area under the concentration-time curve (AUC) was observed. The nonlinear drug exposure (AUC) was likely the result of an antigen sink effect and an uneven frequency of anti-MEDI-546 antibody formation across dose groups. In most dose groups, the elimination half-life of MEDI-546 was less than a week.

Tissue cross reactivity studies with MEDI-546 supported the cynomolgus monkey as a relevant toxicology model. The distribution of MEDI-546 specific staining on the panel of cynomolgus tissues was similar to the staining of human tissues. MEDI-546-specific staining on both human and cynomolgus monkey tissues was present in epithelium, endothelium, mesothelium, mononuclear cells, spindloid/dendritic cells, and intravascular and leaked proteinaceous material (serum) throughout the tissue panels examined. MEDI-546 also stained myenteric plexi in the gastrointestinal tract, glomerular tuft cells in the kidney, granulosa cells in the ovary, beta cells in the pancreas, chief cells of the parathyroid, endocrine cells and pituicytes in the pituitary, decidual cells in the placenta, and spermatogenic cells in the testis in both the human and cynomolgus monkey tissue panels. The staining reported in these studies is consistent with published reports of broad expression of IFNAR in tissues.

A GLP 9-month dose toxicity study in cynomolgus monkeys (6/sex/dose group) where MEDI-546 was administered by IV infusion or SC injection at the dose levels (0, 5, 50, 15, 60 mg/kg/dose), once weekly for 39 weeks. The control group received once weekly IV infusion and SC injection of formulation buffer. Necropsies were performed three days or 13 weeks following the final dose. Toxicity was assessed based on physical examination and clinical signs, dermal irritation, body weight, qualitative food consumption, ophthalmic exam, ECG, blood pressure, semen analysis, immunophenotyping, hematology, coagulation, clinical chemistry, urinalysis, organ weight, macroscopic and microscopic organ/tissue data.

In a total of 5 male animals (5/24, 21%) and 0 female animals (0/24, 0%) exposed to MEDI-546, there were histopathology signs of focal arteritis in small and medium sized arteries. The severity grades of the arteritis ranged from 1 to 3 on a 5-point scale, with Grade 2 findings most frequent. The arteritis was characterized as focal/segmental, with both normal and

affected arteries within each tissue section. It was manifest primarily by intramural and perivascular infiltrates of lymphocytes and macrophages, without necrosis, giant cells or granulomas. Several tissue types/organs were affected, the kidney and gut most frequently, and with no lesions in glomeruli.

In three animals in the high dose 50 mg/kg IV group, effects of Grades 1, 2 and 3 were seen, with Grade 3 findings in one animal only. In one animal in the 60 mg/kg SC group, Grade 2 effects were seen, while one animal in the 5 mg/kg IV group had Grade 2 effects in the arteries of one eye only. Though a vasculitis background incidence of 1-6% has been noted in the literature for this species, no control animal tissues showed vascular pathology and there were no other significant pathology findings attributable to MEDI-546 administration.

Additional details in the nonclinical experience with MEDI-546 are provided in the Investigator's Brochure.

1.4 Clinical Experience with MEDI-546

A phase 1 clinical study (MI-CP 180) was initiated on September 1, 2009 and is presently active. As of 14 July 2010 a total of 17 subjects have been enrolled into the study and dose escalation has progressed through cohort 5, (10.0 mg/kg).

On 14 July 2010 an interim analysis of cumulative data on PK and type I IFN gene signatures was completed on all subjects treated through the completion of Study Day 14 of Cohort 4 to determine whether dose adjustments needed to be made in the multiple dose cohorts (Dose Cohorts 6-8). The PK and PD data from the single dose cohorts was modeled to predict PK profiles and PD response with various doses given weekly \times 4 as described in the protocol. The results indicate that doses of 0.3, 1.0 and 5.0 mg/kg respectively, best target the pre-specified criteria as defined in the protocol of one dose that provides incomplete inhibition of type I IFN gene signature defined as \geq 70% inhibition in $<$ 3 patients per cohort, one dose that provides nearly complete inhibition of type I IFN gene signature defined as \geq 70% inhibition in at least 3 subjects per cohort, and one dose that is approximately $\frac{1}{2}$ log higher than the dose that provides nearly complete inhibition of type I IFN gene signature.

To date the safety profile is acceptable to continue further clinical testing.

1.5 Rationale for Study

Recent research data suggest a potential role of type I IFNs in disease pathogenesis of scleroderma. Therefore, type I IFN inhibition may be efficacious in the treatment of this disease. Scleroderma is an uncommon, complex, systemic fibrosing autoimmune disease characterized by activation of the immune system with macrophage, T-cell, and B-cell abnormalities and autoantibodies, an obliterative proliferative small vessel vasculopathy, and excessive deposition of collagen I and III and other extracellular matrix components. Type I IFN levels are elevated in the serum of patients with scleroderma (Hooks, 1979; Ytterberg, 1982). In addition, increased expression of type I IFN-induced genes and proteins has also been observed in blood and skin of patients with scleroderma (Tan, 2006; Coelho, 2007; York, 2007; Whitfield, 2003).

The actions of type I IFNs are mediated by specific cell surface receptors and JAK-STAT signal transduction pathways. Type I IFNs share the same receptor complex consisting of 2 chains, IFNAR1 and IFNAR2. MEDI-546 is a fully human IgG1 κ monoclonal antibody directed against type I IFNAR1. Type I IFNs bind to IFNAR, which is widely expressed on most cells at low levels (Mogensen, 1999). Recent research data suggest a potential role of type I IFNs in disease pathogenesis of a number of autoimmune disorders that includes scleroderma, SLE, and myositis. Therefore, type I IFN inhibition may be efficacious in the treatment of these diseases.

The proposed study is a Phase 1, multicenter, open-label, dose-escalation trial to evaluate the safety and tolerability of single IV doses (0.1, 0.3, 1.0, 3.0, 10.0 and 20 mg/kg) and multiple IV doses (0.3, 1.0, and 5.0 mg/kg) of MEDI-546 in subjects with scleroderma who have skin thickening in an area suitable for repeat biops. In addition to PK and IM evaluations, the binding of MEDI-546 to type I IFNAR1-bearing cells will be monitored by a receptor occupancy assay. This study will also test neutralization of type I IFN gene expression in whole blood and skin of subjects. The planned starting dose of 0.1 mg/kg corresponds to the human equivalence dose of the primate pharmacologically active dose of 0.3 mg/kg, which is associated with minimal receptor occupancy and target neutralization and is 100-fold lower than the highest dose (30 mg/kg/week \times 4 weeks) administered in the one month repeated-dose study in cynomolgus monkeys.

2 Study Objectives and Overview

2.1 Primary Objective

The primary objective of this study is to evaluate the safety and tolerability of single and multiple IV doses of MEDI-546 in adult subjects with scleroderma who have skin thickening in an area suitable for repeat biopsy.

2.2 Secondary Objectives

The secondary objectives of this study are:

- 1) To evaluate the pharmacokinetics of MEDI-546;
- 2) To evaluate the immunogenicity of MEDI-546; and
- 3) To evaluate the pharmacodynamics of MEDI-546. Type I interferon gene signature in whole blood and involved skin, and subunit 1 of the type I interferon receptor occupancy in whole blood will be used as the PD markers.

2.3 Exploratory Objectives

The exploratory objectives of the study are:

- 1) To evaluate the effect of MEDI-546 on measures of disease activity and patient-reported outcomes;
- 2) To evaluate the effect of MEDI-546 on the expression of other genes and/or proteins in whole blood, serum, and skin and on immunohistopathology of the skin; and
- 3) To evaluate whether DNA polymorphisms in type I IFN-related genes are associated with safety of MEDI-546.

2.4 Overview

Study Design

This is a Phase 1, multicenter, open-label, dose escalation study to evaluate the safety and tolerability of single and multiple IV doses of MEDI-546 in adult subjects with scleroderma who have skin thickening in an area suitable for repeat biopsy. Approximately 10 to 20 sites in North America will participate in the study. A minimum of 33 evaluable subjects are planned for the study, with cohorts of subjects receiving 1 of 6 single IV doses (0.1, 0.3, 1.0,

3.0, 10.0, or 20.0mg/kg) followed by 3 cohorts of subjects receiving 1 of 3 multiple IV doses (0.3, 1.0, or 5.0 mg/kg weekly \times 4) of MEDI-546 as described in [Figure 2.4-1](#); an additional single-dose cohort (Dose Cohort 9, 20 mg/kg) has been included to evaluate safety and tolerability at this dose. The single ascending dose Cohort 9 will enroll simultaneously to the multiple ascending dose cohorts (Cohorts 6, 7, and 8). Simultaneous dosing of Cohort 9 to Cohorts 6, 7, and 8 may occur as cumulative safety data of the lower single ascending dose cohorts (Cohorts 1-5) were evaluated for safety and progression to higher doses approved; the multiple ascending dose cohorts 6, 7, and 8 (0.3, 1.0, 5.0 mg/kg respectively) are lower doses than Cohort 9. The starting dose level will be 0.1 mg/kg administered as a single IV dose. Rules for dose escalation are provided in [Section 4.9](#). Subjects are considered evaluable for safety if they receive MEDI-546 and complete the required evaluations through Study Day 7 or if they discontinue MEDI-546 for safety reasons. In addition, subjects are considered evaluable for the exploratory endpoints if they receive MEDI-546 and complete the required evaluations through Study Day 28. Nonevaluable subjects may be replaced for reasons other than safety to maintain the stipulated cohort sizes in each dose cohort.

If there is a possible safety signal from the analysis of safety information for a particular dose cohort (Dose Cohorts 2-9 only) that does not warrant discontinuation but does warrant further investigation (prior to dose escalation for Dose Cohorts 2-7), then the sponsor may add 4 subjects to the dose cohort for a maximum of 8 subjects in the dose cohort. A maximum of 2 dose cohorts may be expanded to a total of 8 subjects each. If a possible safety signal occurs subsequent to expansion of 2 dose cohorts to a maximum of 8 subjects each, then the study will be terminated. In addition, Dose Cohorts 2-8 may be expanded by up to 2 additional subjects each if eligible subjects are already in screening at the time 4 subjects have been entered into the dose cohort and there is no possible safety signal to warrant expansion of the dose cohort to a maximum of 8 subjects. Therefore, the maximum number of subjects allowed in the study is 53 ($33 + 8 [4 \times 2] + 12 [2 \times 6]$).

MEDI-546 will be administered as an IV infusion over at least 60 minutes for IV doses of ≤ 10 mg/kg or over at least 120 minutes for IV doses of > 10 mg/kg. For doses > 10 mg/kg and for subjects weighing > 250 lbs. or 114 kg please call the medical monitor to discuss the infusion rate instructions. Single-dose IV administration of MEDI-546 will occur on Study Day 0, with follow-up through Study Day 84; multiple-dose IV administration of MEDI-546 will occur on Study Days 0, 7, 14, and 21, with follow-up through Study Day 105.

Subject Evaluation/Follow-up

Screening evaluations will be performed within 28 days prior to MEDI-546 administration. Safety evaluations will be performed from the time the informed consent is signed through end of study and will include history and physical examinations, assessment of AEs and SAEs, monitoring of laboratory tests including hematology, serum chemistry, and urinalysis, safety biomarkers in any subject who has a Grade 1 or higher infusion reaction (including serum levels of mast cell tryptase, cytokines/chemokines, and IgE antibodies), and viral monitoring. Pharmacokinetics (PK), IM, and receptor occupancy will be assessed throughout the study. Receptor occupancy and level of type I IFN gene signature in whole blood and skin will be determined to assess the PD effect of MEDI-546. Clinical outcomes will be evaluated.

The schedule of subject evaluations for subjects receiving single IV doses of MEDI-546 (Dose Cohorts 1-5 and 9) is presented in [Table 3.5-1](#); the schedule of subject evaluations for subjects receiving multiple IV doses of MEDI-546 (Dose Cohorts 6-8) is presented in [Table 3.5-2](#).

[figure not shown]

Figure 2.4-1 Study Flow Diagram

3 Study Procedures

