 - Exploratory correlative studies and storage (serum)

- DNA sample (optional)
- 7) Assess health assessment questionnaire-disability index (HAQ-DI) with scleroderma numeric rating scales (may be done up to 72 hours prior to dosing and preferably prior to the mRTSS and the European disease activity index [DAI] and MEDI-546 administration)
- 8) Assess mRTSS (may be done up to 72 hours prior to dosing)
- 9) Assess European DAI (may be done up to 72 hours prior to dosing)
- 10) Skin biopsy for type I IFN-inducible genes and exploratory analyses (prior to MEDI-546 administration and may be done anytime between signing of the informed consent and Study Day 0)
- 11) Monitor vital signs within 60 minutes before administration of MEDI-546
- 12) **Administration of MEDI-546**
- 13) Monitor vital signs about every 15 minutes during infusion, immediately after the end of the infusion, and about every 30 minutes after the end of the infusion for 2 hours or until stable, whichever is later. Monitor blood pressure and heart rate prior to discharge from the study site.
- 14) Blood collection at 0.5 hours post end of infusion
 - MEDI-546 serum concentration
 - Receptor occupancy
- 15) Monitor for AEs and SAEs

Study Day 1

All Dose Cohorts

- 1) Monitor vital signs
- 2) Monitor for AEs and SAEs
- 3) Record concomitant medications
- 4) Collection of blood
 - MEDI-546 serum concentration
 - Receptor occupancy analysis
 - Type I IFN-inducible genes, exploratory analyses, and storage
 - Exploratory correlative studies and storage (serum)

Study Day 7 (\pm 1 day)

All Dose Cohorts

- 1) Monitor vital signs
- 2) Monitor AEs and SAEs
- 3) Record concomitant medications
- 4) Collection of blood and urine prior to MEDI-546 administration, if applicable
 - Serum chemistry
 - Hematology
 - Urinalysis
 - MEDI-546 serum concentration
 - Receptor occupancy analysis
 - Type I IFN-inducible genes, exploratory analyses, and storage
 - Exploratory correlative studies and storage (serum)

Dose Cohorts 1-5 and 9 only

- 5) Skin biopsy for type I IFN-inducible genes and exploratory studies

Dose Cohorts 6-8 only

- 6) Urine β HCG prior to MEDI-546 administration
- 7) Monitor vital signs within 60 minutes before administration of MEDI-546
- 8) **Administration of MEDI-546**

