4.9 Dose Escalation

Dose Cohort 1 (0.1 mg/kg MEDI-546 as a single IV dose to a single subject) will be started first. Decisions regarding dose escalation will be made by the medical monitor based on the review of all cumulative safety information from the stipulated number of subjects in the preceding lower dose cohort through Study Day 7 for single-dose cohorts (Dose Cohorts 1-5) or Study Day 28 for multiple-dose cohorts (Dose Cohorts 6 and 7) and all cumulative safety data available in all other cohorts.

If there is a possible safety signal from the analysis of safety information for a particular dose cohort (Dose Cohorts 2-9 only) that does not warrant discontinuation but does warrant further investigation prior to dose escalation, then the sponsor may add 4 subjects to the dose cohort for a maximum of 8 subjects in the dose cohort. A maximum of 2 dose cohorts may be expanded to a total of 8 subjects each. If a possible safety signal occurs subsequent to expansion of 2 dose cohorts to a maximum of 8 subjects each, then the study will be

terminated. The SMC, which includes physicians external to MedImmune, will independently review cumulative safety surveillance data and the medical monitor's decisions on dose escalation throughout the study and make recommendations regarding the study progression. The SMC can stop study entry and dosing as it deems necessary.

4.10 Monitoring of Dose Administration As with any foreign protein, infusion reactions and IgE-mediated allergic reactions to dose administration are possible. Therefore, appropriate drugs, such as epinephrine and diphenhydramine, and medical equipment to treat acute anaphylactic reactions must be immediately available, and study personnel must be trained to recognize and treat infusion reactions and allergic reactions such as anaphylaxis.

However, subjects should not be premedicated routinely, because the primary objective of this study is to evaluate the safety and tolerability of the investigational product. If infusion reactions or allergic reactions occur during or after investigational product administration, they should be treated appropriately. If a subject experiences an infusion reaction, premedication according to the physician's judgment should be considered prior to subsequent infusions.

5 Statistical Considerations

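### Safety evaluability ends at Study Day 7 for every cohort, which does not match the Day 28 escalation review of the four-dose Cohorts 6 and 7

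*Protocol*

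**What the plan says.** The Study Abstract, Section 2.4 and Section 3.2 carry the same safety rule: "Subjects are considered evaluable for safety if they receive MEDI-546 and complete the required evaluations through Study Day 7", with discontinuation for safety reasons as the alternative route. No separate rule is given for the multiple-dose cohorts. Section 2.4 then adds a second definition: "subjects are considered evaluable for the exploratory endpoints if they receive MEDI-546 and complete the required evaluations through Study Day 28". The replacement sentence follows directly: "Nonevaluable subjects may be replaced for reasons other than safety to maintain the stipulated cohort sizes in each dose cohort". It does not say which of the two definitions it refers to.

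For Cohorts 6-8, "multiple-dose IV administration of MEDI-546 will occur on Study Days 0, 7, 14, and 21". Under Section 4.9, and likewise Section 3.2, the medical monitor decides on escalation from "review of all cumulative safety information from the stipulated number of subjects in the preceding lower dose cohort", through Day 7 for single-dose cohorts "or Study Day 28 for multiple-dose cohorts (Dose Cohorts 6 and 7) and all cumulative safety data available in all other cohorts". The stipulated number is four for each of Cohorts 6 and 7. Section 10 gives the reason for choosing Day 28: the decision should rest on subjects who had all four doses.

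**The concern.** The escalation review is set at the end of the four-dose course, but the rule for who counts as evaluable stops at a point suited to a single dose. Nothing in the protocol requires a multiple-dose subject to have had four doses, or to have reached Day 28, in order to count for safety. The review can therefore include a subject whose exposure ended after two or three doses, with no clear right to replace that subject.

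The multiple-dose cohorts exist to show how repeated dosing is tolerated, so the later doses matter most. Section 1.3 reports that one of three re-dosed monkeys had a hypersensitivity-like reaction, strongest at the third administration (an isolated case, not seen again in the one-month study). In Table 3.5-2 the first anti-drug antibody sample after dosing is on Day 28, and the Day 7 laboratory samples are taken before dose 2: "Collection of blood and urine prior to MEDI-546 administration, if applicable". Safety evaluability at Day 7 thus captures little of what these cohorts were added to show.

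**Working it through.** **Step 1. Apply the written rules to a subject in Cohort 6 or 7.**

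| Course of events | Safety-evaluable (Day 7)? | Exploratory-evaluable (Day 28)? | Result |
|---|---|---|---|
| Leaves before completing Day 7, non-safety reason | No | No | Replaceable |
| Stops dosing after Day 7, non-safety reason, stays through Day 28 | Yes | Yes | Fills a place with two or three doses |
| Leaves the study between Day 7 and Day 28, non-safety reason | Yes | No | Unclear |
| Stops drug for safety | Yes, by definition | Depends on follow-up | Counts for safety |

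The second row is a real route. Section 3.5 keeps treated subjects on the visit schedule however few doses they had. Section 4.7 follows those permanently taken off drug to Day 105 unless consent is withdrawn. Section 4.5 gives a non-safety example: a subject who intends to become pregnant has no further doses but is followed. The Day 28 definition asks for receipt of drug and completed evaluations, not for a number of doses, so this subject is evaluable under both definitions.

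**Step 2. Count doses at Day 7.** Section 3.5 places the second infusion and the two hours of vital signs after it within the Day 7 visit. A subject who completes that visit has had two of four doses.

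**Step 3. Reproduce the protocol's own figure.** Table 5.2-1, N = 4, true event rate 10%: P(at least one event) = 1 − 0.90^4 = 1 − 0.6561 = 34.4%. This agrees with the table.

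**Step 4. Chance of fewer than four fully dosed subjects.** Let d be the chance that a subject does not complete the four doses. Assume that subjects are independent and none is replaced. The protocol gives no value for d; 5% to 15% is assumed.

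- One cohort of four, 1 − (1 − d)^4: d = 5% gives 1 − 0.8145 = 18.5%; d = 15% gives 1 − 0.5220 = 47.8%.
- At least one of Cohorts 6 and 7, 1 − (1 − d)^8: d = 5% gives 1 − 0.6634 = 33.7%; d = 15% gives 1 − 0.2725 = 72.8%.

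**Step 5. What one missing subject costs, for information on the full schedule.**

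- Chance of seeing an event with a true 10% rate: 1 − 0.90^4 = 34.4% with four subjects, 1 − 0.90^3 = 27.1% with three.
- Upper limit of the exact two-sided 95% interval after zero events, 1 − 0.025^(1/n): 60.2% for n = 4, 70.8% for n = 3.

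**The case against.** The strongest reply is that Section 4.9 does not refer to the Day 7 rule at all. It asks for the stipulated number of subjects through Day 28, which can be read as four subjects observed to Day 28. The medical monitor decides, and the safety monitoring committee reviews each decision and can stop dosing. The footnote to Figure 2.4-1 also deals with Day 28 escalation according to Appendix 5; the figure was not available for this check and should be consulted. This stands to the extent that the protocol nowhere expressly allows escalation on three or fewer fully dosed subjects. It does not remove the mismatch: a subject followed to Day 28 after two doses satisfies that reading of Section 4.9 and still misses the purpose in Section 10. Oversight supplies no minimum number either.

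Two stronger readings are tempting and not supported. A reader might infer that anyone who drops out after Day 7 cannot be replaced. The replacement sentence follows the Day 28 definition and is not limited to safety, so for a subject who leaves the study the text is ambiguous, not prohibitive. A reader might also infer that Day 7 means one dose only; Step 2 shows that it means two for anyone who completes the visit.

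It is also fair to say that a partly dosed subject still gives safety information, so the fall from 34.4% to 27.1% applies only to events that need the full schedule to be seen. The repeat skin biopsy is not simply lost, since Section 3.7 asks for it at discontinuation, though after fewer doses. The option of up to two extra subjects helps only if they are already in screening when four have been entered.

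**Conclusion.** The point holds as a mismatch between stated rules. The Day 7 definition was not adapted to Cohorts 6-8, it conflicts with the Day 28 review and that review's stated purpose, and the replacement rule is unclear for subjects who leave between Day 7 and Day 28. Subjects who stop dosing after Day 7 for a non-safety reason but remain in follow-up do count as evaluable and do fill a place.

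The size depends on an assumed 5-15% rate of incomplete dosing, independence between subjects, and no replacement. On that basis it is 18.5-47.8% per cohort and 33.7-72.8% for at least one of Cohorts 6 and 7. Adding Cohort 8 would give 1 − 0.95^12 = 46.0% to 1 − 0.85^12 = 85.8%, but no multiple-dose escalation follows Cohort 8, so that range should not be used for this question. There is no formal sample size calculation for the gap to undermine. It is a worthwhile and inexpensive correction, best made before the first multiple-dose escalation decision, and not a defect that invalidates the design.

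**What to change.** Reconcile the evaluability and replacement text in the Study Abstract and Sections 2.4 and 3.2 with the escalation text in Sections 3.2 and 4.9:

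- keep Day 7 as the safety-evaluability point for the single-dose cohorts;
- for Cohorts 6-8, align safety evaluability with the Day 28 review and its stated complete-schedule purpose, keeping discontinuation for safety reasons as the alternative route;
- state how a subject who misses an infusion for a logistical reason but completes Day 28 is counted, so that the new wording does not create a fresh ambiguity;
- state which kind of nonevaluability, safety or exploratory, permits replacement.

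This changes who counts and who may be replaced; it does not change dosing. All treated subjects stay in the safety summaries under Section 5.3. The cost is one amended definition, possibly one or two replacements under the existing rule, and a short delay while they complete follow-up.
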